### Section 9 - RESEARCH PROGRESS

A. Summarize the progress of the research, including any interim findings.

**To date, we have consented 34 participants. Recruitment was significantly slowed due to COVID-19 study suspensions and time needed to ensure study procedures conformed to research activity requirements introduced due to the COVID-19 pandemic.**

B. For multi-site studies, summarize the overall progress of the research. *Attach a copy of the most recent multi-site study report, if any.*

N/A

C. Summarize any IRB-approved amendments or changes made to the research since last IRB review (initial or continuing). If IRB approval was not obtained for changes, provide an explanation.

N/A

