## Section 10- NUMBER OF PARTICIPANTS

*The number of participants is defined as the number of individuals who agreed to participate (i.e., those who provided consent or whose records were accessed, etc.) even if all do not prove eligible or complete the study. The total number of research participants may be increased only with prior IRB approval.*

a. Is this a multi-site study?  Yes → Indicate the total number of participants to be enrolled across all sites: \_\_\_\_\_

No

b. For research approved by an Kent State University IRB, provide:

1) IRB approved number of participants (or records, specimens, etc.): \_\_\_\_\_

64

2) Total number of participants enrolled in the research to date: \_\_\_\_\_

34

3) Number of participants enrolled since last IRB review (initial or continuing): \_\_\_\_\_

4

c. If the actual total enrollment to date is significantly different (over or under) from IRB approved number, provide an explanation:

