# Research participants wanted for a study assessing strategies to control drinking.

## Participants must:

- Be 21 years or older
- Drink alcohol regularly
- Own a smart phone

In this study we will ask you to complete a two hour session at Kent State University that includes questions related to alcohol use, symptoms of anxiety or depression, and neuropsychological tasks that measure your cognitive performance. At the end of this session we will explain techniques for controlling or limiting your drinking – if you choose to do so. Then we will ask you to monitor your drinking (how many drinks per day you have) for a two-week period. Finally, we will send you a link to complete outcome measures asking the same questions you completed in the laboratory session – this will take about two hours to complete. All sessions are completely confidential.

**Compensation:** Participants will be compensated \$40 for completing the first 2-hour session at Kent State and an additional \$40 for completing the final assessment online - \$80 in total.

If you are interested, please contact study personnel via email or phone:

[[contact]](mailto:[contact])

[contact]

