Participants will be recruited using the Kent State University SONA system and from the community via flyers and online advertisement. Eligible participants will meet the following inclusion criteria 1) be age 21 or older, 2) report experiencing at least three negative consequence of alcohol use in the past month (assessed via Brief Young Adult Alcohol Consequences Questionnaire: BYAACQ), 3) report having consumed at least 5 drinks (for men) or 4 drinks (for women) on one or more occasions in the past 2-weeks 4) not be seeking treatment for alcohol use from a health-care provider, and 5) have access to a smartphone and 6) endorse some importance in changing their drinking (2 or greater on Alcohol Ladder Scale importance to change). Participants who endorse seeking treatment for alcohol related problems from a health care provider will be provided with a list of university sponsored and community based treatment providers.

Participants (n=64) will complete a battery of assessments detailed below including (1) demographic measures, (2) alcohol and substance use measures, (3) psychological measures, (4) behavioral economic and (5) neuropsychological measures.

**(1) Demographic Measures:** will include brief questions about demographic characteristics biological sex, race, and socio-economic status.

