**(2) Alcohol and Other Substance Use:** The Timeline Follow-back Interview will be used to assess alcohol use over the prior 30 days[1]. The Implicit Association Test is a reaction time task requiring participants to manipulate alcohol related stimuli and has been shown to be a reliable measure of automatic impulses to drink alcohol [2, 3]. The Young Adult Alcohol Consequences Questionnaire (YAACQ ) will be used to assess a range of negative consequences of alcohol use that young adults may experience (e.g., while drinking in the past month, I have said or done embarrassing things). Assessment of Diagnostic and Statistical Manual of Psychiatric Disorders V (DSM-V)[4] alcohol related symptoms (e.g. During the times when you drank alcohol, did you end up drinking more than you planned when you started?). The Drinking Motive Questionnaire Revised Short Form (DMQ-R SF): assesses motives for drinking in adolescents and young adults in four categories (social, coping, enhancement, social pressure)[5]. The Alcohol Expectancies Brief[6] measures positive and negative expectancies of alcohol use. Alcohol Contemplation Ladder is a measure of importance and motivation to make a change in one's alcohol consumption[7]. Smoking History/Dependence Questionnaire: Smoking history and life smoking patterns will be assessed as recommended by the National Cancer Institute consensus panel (e.g. have you ever used tobacco products; how often do you use tobacco products). The Self-Report Habit Index (SRHI) measures adult habitual substance use . Additional questions regarding substance use history (specifically pertaining to age of onset and frequency of use for various illicit/unregulated substances) will also be administered.

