**(3-5) Neuropsychological, Behavioral Economic, and Psychological Measures:** Working Memory Performance and Inhibition will be measured using the National Institute of Health Examiner (Executive Abilities) [8]. The Monetary Choice Questionnaire (Delay Discounting) is a behavioral economic measure for assessing state in subjective value of delayed rewards, with greater discounting of value indicative of decreased self-control[9, 10]. Psychological Measures: will include The UPPS-P Impulsive Behavior Scale: a self-report that assesses five subscales that are used to measure distinct dimensions of impulsive behavior[11]. The Difficulties in Emotional Regulation Scale (DERS) will be used to measure the ability to utilize several emotion regulation strategies. The Positive and Negative Affect Scale will be administered to measure changes in affect[12]. Symptoms of depression, anhedonia, and anxiety will be assessed using the Center for Epidemiologic Studies –Depression Scale (CES-D)[13], SHAPS Anhedonia scale[14], and Generalized Anxiety Disorder 7-item (GAD-7)[15].

Following this initial baseline assessment, participants will be randomized to one of two experimental conditions detailed below. If they are randomized to Alcohol Moderation Group 1 they will receive a link to access the Alcohol Moderation software via smartphone, and a brief demonstration on how to utilize the application will be provided by trained research assistants. Participants will be asked to use the application if they consume alcohol at any point during the two-week observation period. Participants will not be encouraged to use alcohol, and will be clearly informed that there will be no penalty for not using the application during a drinking session or not drinking at all during the two-week observation period.

**Alcohol Moderation Group 1:** Alcohol Moderation group 1 will be introduced to alcohol moderation strategies developed by the National Institute on Alcohol Abuse and Alcoholism. In addition to introducing participants to these drinking moderation strategies they will be asked to download and utilize the Social Drinker application, which addresses many of the strategies. A full description is listed below.

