**Avoid "triggers."** What triggers your urge to drink? If certain people or places make you drink even when you don't want to, try to avoid them. If certain activities, times of day, or feelings trigger the urge, plan something else to do instead of drinking. If drinking at home is a problem, keep little or no alcohol there.

**Plan to handle urges.** When you cannot avoid a trigger and an urge hits, consider these options: Remind yourself of your reasons for changing (it can help to carry them in writing or store them in an electronic message you can access easily). Or talk things through with someone you trust. Or get involved with a healthy, distracting activity, such as physical exercise or a hobby that doesn't involve drinking. Or, instead of fighting the feeling, accept it and ride it out without giving in, knowing that it will soon crest like a wave and pass. Also, see the short module to help you handle urges to drink.

**Know your "no."** You're likely to be offered a drink at times when you don't want one. Have a polite, convincing "no, thanks" ready. The faster you can say no to these offers, the less likely you are to give in. If you hesitate, it allows you time to think of excuses to go along. Also, see the short module to help you build drink refusal skills.

Following the two week observation period participants will repeat baseline assessment procedures including: (2) alcohol and substance use measures, (3) psychological measures, (4) Behavioral Economic and (5) neuropsychological measures. Additionally, participants will complete questionnaires assessing their experience while using 1) the moderation strategies detailed above and 2) [for participants using the mobile application] specific questions regarding use of the application (e.g. The mobile application was easy to use; I would use this mobile application to help monitor my alcohol use). The follow-up measures will be administered via email and collected through Qualtrics online survey platform.

---

3f. Check all research activities that apply. *Attach a copy of materials to be used (e.g., interview/focus group questions, instruments, data collection forms, etc.).*

 Anesthesia (general or local) or sedation	 Magnetic Resonance Imaging (MRI)
 Audio, video, digital, or image recordings	 Materials that may be considered sensitive, offensive, threatening, or degrading

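### The consequences questionnaire looks back a month but is repeated after two weeks, so about half of its recall precedes randomisation and the percentage reduction is understated

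*Protocol*

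**What the plan says.** The aims (IRB application, Section 3, 3c) put user experience and willingness to use the app first. Initial efficacy in reducing negative consequences of drinking is the secondary objective.

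Under 3e, item (2), the only example item for the consequences questionnaire reads "while drinking in the past month, I have said or done embarrassing things". The brief version used for eligibility has the same window: participants must "report experiencing at least three negative consequence of alcohol use in the past month". Timeline Follow-back covers the prior 30 days.

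On timing, 3e states: "Following this initial baseline assessment, participants will be randomized to one of two experimental conditions detailed below". It then states: "Following the two week observation period participants will repeat baseline assessment procedures including: (2) alcohol and substance use measures". The recruitment text describes the final assessment as "outcome measures asking the same questions you completed in the laboratory session". On delivery, 3e says: "The follow-up measures will be administered via email and collected through Qualtrics online survey platform". No date by which the emailed link must be completed is given.

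The recruitment text also asks participants to monitor the number of drinks each day for the two weeks. The continuing review, Section 9, reports that "we have consented 34 participants"; the approved number is 64.

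**The concern.** The intervention can act only after randomisation, and the first follow-up reply comes two weeks later. A questionnaire that looks back a month then mixes days the app could influence with days it could not, and the second group was already reported at baseline. A total score cannot be split by date afterwards, so this is settled when the data are collected and cannot be repaired in the analysis.

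What is at stake is how the efficacy result is read. A real reduction would appear as a smaller percentage fall than the one that occurred, and a later trial planned on that percentage would be planned on too small a figure. Because the link is emailed with no completion window, the number of pre-randomisation days also differs between participants according to when they reply.

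**Working it through.** **Inputs.** From the protocol: past-month recall (3e item (2); taken as 30 days, with 28 and 31 as limits), randomisation after baseline (taken as day 0), and follow-up after two weeks (day 14 at the earliest). Assumed: the same window at follow-up, events spread evenly over days, and the event rates named below. The protocol gives no figure for the overlap, so there is none to reproduce.

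**Step 1, overlap.** Pre-randomisation days = window − reply day.

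| Reply day | Pre-randomisation days of 30 | Post-randomisation share |
|---|---|---|
| 14 | 16 | 14/30 = 47% |
| 17 | 13 | 17/30 = 57% |
| 21 | 9 | 21/30 = 70% |
| 28 | 2 | 28/30 = 93% |

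On day 14 a 28-day month gives 14 days (50%) and a 31-day month gives 17 (55%).

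**Step 2, percentage fall after a complete stop.** For single-occurrence events the average fall equals the post-randomisation share: 14/30 = 47% on day 14. This is an average and not a ceiling. Of participants with three such consequences (the eligibility minimum), dated independently, (14/30)³ = 10% would show none at follow-up and (16/30)³ = 15% would still show all three.

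For a recurring yes/no item with daily probability p (assumed), the day-14 fall is 1 − [1 − (1−p)^16] / [1 − (1−p)^30]:

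- p = .01: 1 − .1485/.2603 = 43%
- p = .03: 36%
- p = .05: 29%
- p = .10: 1 − .8147/.9576 = 15%

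**Step 3, raw group difference, event counts.** Baseline covers days −30 to 0 and a day-14 follow-up covers days −16 to 14. In the change score the shared 16 days cancel, leaving days 0 to 14 minus days −30 to −16. With a common daily rate before randomisation and rates a and b in the two arms afterwards, the expected group difference in change is 14(a − b), exactly what a 14-day window gives. What shrinks is the percentage: if λ is the earlier rate, the fall in an arm with later rate a is (14/30)(1 − a/λ). A true 30% cut (assumed) would show as 0.30 × 14/30 = 14%.

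**Step 4, raw group difference, yes/no items.** An item already true in the earlier 16 days cannot be changed by the app. With Poisson events at μ expected occurrences per month, the past-month group difference is exp(−16μ/30) times the 14-day difference:

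- μ = 0.3: 85%
- μ = 1: 59%
- μ = 3: 20%

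The raw difference is therefore reduced for this format, by an amount that depends on how often the events recur.

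**Step 5, window for a remedy.** An open-ended window running from the first session would lengthen with reply day. At p = .01, endorsement is 1 − .99^14 = .131 on day 14 and 1 − .99^21 = .190 on day 21, with no treatment effect at all. An added version needs a fixed end.

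**The case against.** The strongest objection is Step 3. The sample-size section (4b) assumes two groups and two repetitions, so the natural contrast is a change score, and for event counts the overlapping days drop out of it. This stands. It limits the point to the percentage or per-day reduction, and to the raw difference only if items are yes/no.

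Second, the past-month window at follow-up rests on one example item and a recruitment text; the instruments themselves are not shown. This stands as a caveat. Against it, the eligibility version uses the same window, the measures are to be repeated, and the protocol does state a two-week window where it wants one (the heavy-drinking inclusion criterion).

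Third, the study is described as a preliminary usability study and efficacy is secondary. This stands and lowers the weight of the point.

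Fourth, the daily monitoring in the recruitment text already covers post-session drinking. That is a fair answer for drinking, but it does not cover consequences.

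A reader might go further and infer that the planned effect of f = .13 shrinks to .13 × 14/30 = .061 and that power collapses. The documents do not support this. They do not say which outcome or recall window f = .13 refers to, nor the correlation between repetitions, and Step 3 shows that the raw difference need not shrink in that proportion.

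**Conclusion.** The point holds in a limited form. On the only window the protocol describes, a day-14 reply draws about 16 of 30 recalled days (14 to 17 across month lengths) from before randomisation. The overlap falls to 9 days on day 21 and 2 on day 28. The percentage or per-day reduction in consequences is understated: a complete stop would show on day 14 as an average fall of about 47% for single-occurrence events, and 43% down to 15% for recurring yes/no items at assumed daily rates of .01 to .10.

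It would be wrong to say that the group difference is shrunk in every case. For event counts it matches that of a 14-day window; for yes/no items it is smaller, and the response format is not stated. No loss of power is claimed. Pre-randomisation days are alike in both arms in expectation, so false positives do not rise, provided reply timing is similar in the two arms. The main objective is unaffected.

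The conclusion assumes an unchanged past-month form at follow-up and evenly spread events. Severity: minor to moderate.

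**What to change.** - **Consequences, participants not yet followed up:** keep the past-month form, add the same items for a fixed window (the 14 days after the first session, with dates shown), and record the completion date. Analyse the 14-day score with the past-month baseline score as covariate, not as a change score, since the two windows differ. Present it as a supporting efficacy estimate.
- **Consequences, all participants:** report the past-month score with a statement that it includes pre-randomisation days.
- **Drinking, all participants:** score follow-up on post-randomisation days only, as a daily rate with the 30-day baseline rate as covariate. Use Timeline Follow-back if it is recorded by day, otherwise the two-week daily monitoring, with the same source in both arms.

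The cost is an IRB wording amendment and a few extra minutes of questionnaire, with no added visit and no loss of past-month data. Late repliers must recall a dated window that has already closed. The covariate analysis departs from the two-repetition framework behind n = 64. With 34 of 64 already consented, 64 − 34 = 30 are still to be enrolled; how many of the 34 await follow-up is not stated. The 14-day score will therefore exist for only part of the sample and be imprecise, and no gain in power should be expected from it.

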### **Alcohol Moderation Group 2:**

Alcohol moderation Group 2 will be exposed to the National Institute of Alcohol Abuse and Alcoholism strategies for moderation, without access to the Social Drinker Application.

*Small changes can make a big difference in reducing your chances of having alcohol-related problems. Whatever strategies you choose, give them a fair trial. If one approach doesn't work, try something else. But if you haven't made progress in cutting down after 2 to 3 months, consider quitting drinking altogether, seeking professional help, or both.*

*Here are some strategies to try, and you can add your own at the end. Identify perhaps two or three to try in the next week or two.*

**Keep track.** Keep track of how much you drink. Find a way that works for you: Carry a drinking tracker card in your wallet, make check marks on a kitchen calendar, or enter notes in a mobile phone notepad or personal digital assistant. Making note of each drink before you drink it may help you slow down when needed.

**Count and measure.** Know the standard drink sizes so you can count your drinks accurately. Measure drinks at home. Away from home, it can be hard to keep track, especially with mixed drinks, and at times, you may

*be getting more alcohol than you think. With wine, you may need to ask the host or server not to "top off" a partially filled glass.*

**Set goals.** Decide how many days a week you want to drink and how many drinks you'll have on those days. It's a good idea to have some days when you don't drink. People who always stay within the low-risk limits when they drink have the lowest rates of alcohol-related problems.

**Pace and space.** When you do drink, pace yourself. Sip slowly. Have no more than one standard drink with alcohol per hour. Have "drink spacers"—make every other drink a non-alcoholic one, such as water, soda, or juice.

**Include food.** Don't drink on an empty stomach. Eat some food so the alcohol will be absorbed into your system more slowly.

**Find alternatives.** If drinking has occupied a lot of your time, then fill free time by developing new, healthy activities, hobbies, and relationships, or renewing ones you've missed. If you have counted on alcohol to be more comfortable in social situations, manage moods, or cope with problems, then seek other, healthy ways to deal with those areas of your life.

**Avoid "triggers."** What triggers your urge to drink? If certain people or places make you drink even when you don't want to, try to avoid them. If certain activities, times of day, or feelings trigger the urge, plan something else to do instead of drinking. If drinking at home is a problem, keep little or no alcohol there.

**Plan to handle urges.** When you cannot avoid a trigger and an urge hits, consider these options: Remind yourself of your reasons for changing (it can help to carry them in writing or store them in an electronic message you can access easily). Or talk things through with someone you trust. Or get involved with a healthy, distracting activity, such as physical exercise or a hobby that doesn't involve drinking. Or, instead of fighting the feeling, accept it and ride it out without giving in, knowing that it will soon crest like a wave and pass. Also, see the short module to help you handle urges to drink.

**Know your "no."** You're likely to be offered a drink at times when you don't want one. Have a polite, convincing "no, thanks" ready. The faster you can say no to these offers, the less likely you are to give in. If you hesitate, it allows you time to think of excuses to go along. Also, see the short module to help you build drink refusal skills.

Following the two week observation period participants will repeat baseline assessment procedures including: (2) alcohol and substance use measures, (3) psychological measures, (4) Behavioral Economic and (5) neuropsychological measures. Additionally, participants will complete questionnaires assessing their experience while using 1) the moderation strategies detailed above and 2) [for participants using the mobile application] specific questions regarding use of the application (e.g. The mobile application was easy to use; I would use this mobile application to help monitor my alcohol use). The follow-up measures will be administered via email and collected through Qualtrics online survey platform.

---

3f. Check all research activities that apply. *Attach a copy of materials to be used (e.g., interview/focus group questions, instruments, data collection forms, etc.).*

 Anesthesia (general or local) or sedation	 Magnetic Resonance Imaging (MRI)
 Audio, video, digital, or image recordings	 Materials that may be considered sensitive, offensive, threatening, or degrading
 Biohazards (e.g., rDNA, infectious agents, select agents, toxins)	 Non-invasive medical procedures (e.g., EKG, Doppler)
 Biological sampling (other than blood)	 Observation of participants (including field notes)
 Blood drawing, injections, surgical procedures (including biopsies)  Complete Appendix Q	 Oral history (does not include medical history)
 Coordinating Center	 Placebo
 Data, not publicly available	 Pregnancy testing
 Data, publicly available	 Radiation (e.g., CT or DEXA scans, X-rays, nuclear medicine procedures)  Complete Appendix V
 Data/Specimen storage/repository  Complete Appendix C (future unspecified use, including research databases for purposes of sharing data or specimens collected with other researchers/studies in the future)	 Record review (which may include PHI)
 Deception  Complete Appendix D & Appendix M1	 Specimen research
 Devices  Complete Appendix E	 Stem cell research
 Diet, exercise, or sleep modifications	 Surveys, questionnaires, or interviews (one-on-one)
 Drugs or biologics  Complete Appendix F	 Other: Specify:
 Emergency research	
 Focus groups	
 Food supplements	
 Gene transfer	
 Genetic testing  Complete Appendix G	
 Internet or e-mail data collection	

3g. Estimate the time required from each participant, including individual interactions, total time commitment, and long-term follow-up, if any.

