Heavy episodic drinking is related to a range of unfavorable outcomes and represents a significant public health problem. Despite experiencing significant negative consequences, the majority of problem drinkers will never seek treatment from a direct care provider (SAMHSA, 2015). Mobile technology has the potential to transform how alcohol interventions are delivered by providing a more direct platform to promote behavior change. Indeed, mobile technologies have demonstrated utility in providing treatment information for a wide-range of behaviors for which individuals often hesitate to seek professional help, including smoking cessation, sexual health, weight management, and anxiety (Cohn, Hunter-Reel, Hagman, & Mitchell, 2011). Moreover, recent research suggests that tools aimed at reducing irresponsible drinking behaviors often fail because they do not account for barriers to treatment implementation caused by the intoxicating effects of alcohol. Alcohol directly affects several underlying neurocognitive mechanisms necessary for adhering to drinking limits (Day et al., 2015; Guillot, Fanning, Bullock, McCloskey, & Berman, 2010; Kahler et al., 2014; [name], 2016). Specifically, alcohol affects the ability to maintain focus on previously defined goals (e.g. I will only have 2 drinks), and to weigh those goals against competing acute reinforcers (pleasurable effects of alcohol) (Houben, Wiers, & Jansen, 2011). Therefore, two major barriers to changing problematic patterns of alcohol use include (1) willingness to seek professional help despite motivation to change, (2) difficulty adhering to pre-defined drinking limits caused by alcohol's intoxicating effects. The current application proposes to test a mobile application with potential to address both of these barriers. First, the mobile application provides an active self-help based platform for moderating alcohol use that is accessible without seeking assistance from a health-care provider. Second, the application provides guidance on moderating alcohol use in real time based on individual users pre-defined drinking limits, which helps reduce demands on the neurocognitive mechanisms that are diminished following alcohol consumption. Specifically, the application utilizes an algebraic formula to proactively pace a user's alcohol consumption over time (provides a visual cue of how much of their current beverage should be remaining, as well as the time remaining until they can start their next drink) based on their predefined drinking limits, as well as individual factors including weight, sex, and other variables affecting the metabolism of alcohol.

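### The remote follow-up repeats the cognitive performance tasks with no stated sobriety condition and no record of hours since the last drink, so those scores may partly reflect alcohol on board

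*Protocol*

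**What the plan says.** Protocol, Section 3 (Research Design), item 3e, lists the tasks. For executive function, "Working Memory Performance and Inhibition will be measured using the National Institute of Health Examiner". For discounting, "The Monetary Choice Questionnaire (Delay Discounting) is a behavioral economic measure for assessing state in subjective value of delayed rewards". Among the alcohol measures, "The Implicit Association Test is a reaction time task requiring participants to manipulate alcohol related stimuli".

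The end of the Group 2 description in 3e has all of these repeated: "Following the two week observation period participants will repeat baseline assessment procedures including: (2) alcohol and substance use measures", followed by the psychological, behavioral economic and neuropsychological categories. On the mode, "The follow-up measures will be administered via email and collected through Qualtrics online survey platform". The recruitment flyer agrees that a link is sent.

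Eligibility in 3e requires that participants "report having consumed at least 5 drinks (for men) or 4 drinks (for women) on one or more occasions" in the past two weeks. They may go on drinking during the observation period. Item 3b gives the scientific premise: "Alcohol directly affects several underlying neurocognitive mechanisms necessary for adhering to drinking limits". Item 3c names executive function as one example of a correlate of change, under the secondary objective.

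**The concern.** The protocol's argument for the app is that drinking weakens goal maintenance and the weighing of goals against immediate reward. Its task battery measures working memory, inhibition and delay discounting, which lie close to those functions. At follow-up the battery is done away from the laboratory, by people selected for heavy episodes. Nothing in the visible text asks whether they have been drinking.

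Two consequences follow for analyses that use follow-up task scores. First, a score taken with alcohol on board partly measures recent drinking, so some of its correlation with drinking outcomes would be an artefact. Second, the app is meant to change drinking, so the share of participants tested with alcohol on board could differ by arm and look like, or hide, a cognitive change. The move from a supervised laboratory session to an unsupervised remote one could also make the contamination differ between the two time points.

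An analysis plan cannot repair this later, because hours since the last drink are not among the data the protocol describes collecting.

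**Working it through.** The protocol gives no figure on this point, so there is none to reproduce. The check is a reading of the text, followed by two illustrations on assumed values.

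**1. Is there a sobriety condition anywhere?** These parts of the protocol were read for an alcohol-free interval, breath test, sobriety question, completion window or time of day: the recruitment flyer, the eligibility criteria and procedures in 3e, the session length in 3g, and the consent process in 8f. None states one.

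**2. What record of drinking exists?** The Timeline Follow-back covers the prior 30 days and, as an alcohol measure, is repeated at follow-up. The flyer adds monitoring of drinks per day for two weeks. Both give days. As described, neither gives hours since the last drink or a check at the moment of testing.

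**3. Can alcohol from a qualifying episode still be present at a session?** Assumptions, none of them in the protocol: the Widmark formula, 14 g of alcohol per drink, distribution factor 0.68 (men) and 0.55 (women), elimination of 0.012 to 0.020 g/dL per hour, and the body weights shown. The drink counts are those of the eligibility criterion.

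Peak (g/dL) = drinks × 14 / (weight in kg × factor × 10). Clearance time = peak / elimination rate, counted from the start of drinking.

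- Man, 80 kg, 5 drinks: 70 / (80 × 0.68 × 10) = 70 / 544 = 0.129 g/dL. At 0.020, 0.015 and 0.012 per hour: 6.4, 8.6 and 10.7 h.
- Woman, 60 kg, 4 drinks: 56 / (60 × 0.55 × 10) = 56 / 330 = 0.170 g/dL. At the same rates: 8.5, 11.3 and 14.1 h.

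With an assumed 20:00 start and the middle rate, alcohol clears at about 04:35 in the man and 07:20 in the woman. At the slowest rate the woman clears shortly after 10:00. Completion on the same evening is therefore the plain case. Carry-over into the next morning is possible but not typical at these values; a later start or more drinks would extend it.

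**4. What could that do to a comparison between arms?** Spurious shift = acute decrement × difference between arms in the share tested with alcohol on board. With an assumed decrement of 0.3 to 0.8 SD and an assumed difference of 10 to 20 percentage points, the range runs from 0.3 × 0.10 = 0.03 SD to 0.8 × 0.20 = 0.16 SD. Both inputs are invented for illustration, so this is not an estimate for this trial.

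**The case against.** The case against is substantial, and much of it stands.

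- **Silence is not permission.** A reader might infer that the follow-up may be completed at any hour, evenings included. The protocol does not say so; it only states no window. Instruments and consent pages are not in view and could carry an instruction. Even so, the eligibility, procedure and flyer text, where such a condition would normally appear, is present and has none.
- **Drinking is recorded.** It would be wrong to say that the trial has no record of recent drinking. Day-level data exist around both sessions and could flag a test done on, or the day after, a drinking day. What is missing is the hour, which separates a test before drinking from one after it.
- **Baseline is different.** A reader might extend the point equally to both sessions. Baseline is in person, with staff taking consent in a private room, so overt intoxication would probably be noticed. It also precedes randomization, so it cannot create a systematic difference between arms.
- **Clearance hours are not bias.** Eligibility needs only one qualifying episode in two weeks. At that minimum, 6.4 to 14.1 h out of 14 × 24 = 336 h is 1.9% to 4.2% of the time. How often participants actually drink, and when they open the link, is unknown.
- **The aims are mostly elsewhere.** User experience is the main objective, and efficacy is judged on negative consequences reported over the past month. Neither is a task score. Item 3c does not say whether correlates are baseline or follow-up values; if only baseline values are used, the follow-up problem does not reach that analysis. No stated aim tests an arm effect on cognition.
- **The premise does not cover every task equally.** Item 3b speaks of holding to goals and weighing them against reward. It does not mention implicit association, where the link is looser.

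What survives is that the plan, run as written, collects follow-up performance scores whose meaning depends on sobriety, with no means of telling afterwards which scores were affected.

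**Conclusion.** The point holds for the remote follow-up and for the performance tasks. Follow-up scores for working memory, inhibition, delay discounting and implicit association may partly reflect alcohol on board, and so may any change or correlate analysis under item 3c that uses them. The size of the bias cannot be derived from the documents. The clearance times of 6.4 to 14.1 hours rest on assumed weights and constants and show only that overlap can occur; the 0.03 to 0.16 SD range rests wholly on assumed inputs.

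A reader might infer that the trial's main results are compromised. The documents do not support that: the user-experience objective and the negative-consequences outcome do not depend on these tasks. The change is worth making because it is cheap and the missing information cannot be recovered later.

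**What to change.** In item 3e:

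- Open the follow-up survey with one item on the time and amount of the last drink. Put the same item at the start of the baseline session for comparability.
- Say in the follow-up email that the performance tasks are to be done when alcohol-free.
- State an interval in advance. If it is not met, defer the performance tasks alone, within a short fixed window, and let the questionnaires proceed as planned. The choice of interval is for the investigators.
- Use the item to flag affected scores for a sensitivity analysis that excludes them. Do not enter it as a covariate in comparisons between arms: it is measured after randomization and may itself be changed by the app, so adjusting for it could introduce bias. Excluding flagged scores also selects on behaviour after randomization, so that analysis should support the main one and not replace it.

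The cost is one item, one line in the email and some tasks done a day later. Self-report will miss some drinking. Deferral ties the timing of the tasks to drinking, which is why the window should be short. The continuing-review form reports 34 of 64 participants enrolled; those 34 may lack the item, and it would serve mainly the remaining 64 − 34 = 30. The dataset should mark which procedure each participant had.
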